2. SPECIFIC AIMS AND OBJECTIVES FOR MAIN TRIAL

This research includes one primary and three secondary specific aims.

Primary Aim

Aim 1: Compare the effectiveness of the 2 arms on weight-for-length and other weight measures through age 2.

Hypothesis 1: Arm 2 will be significantly better than Arm 1 in supporting healthy child weight-for-length trajectory over 2 years.

Secondary Aims

Aim 2: Compare the effectiveness of the two approaches on parent-reported outcomes, including child feeding and physical activity behaviors, parent feeding beliefs and behaviors, media use, and quality of doctor-parent communication.

Hypothesis 2: Arm 2 will be significantly better at improving parent-reported health behaviors.

Aim 3: Examine differences in main outcomes by social determinants, including race/ethnicity, language, health literacy.

Hypothesis 3: A literacy- and culturally-sensitive approach to obesity prevention will result in equal subgroup improvements.

Aim 4: To compare weight-for-length trajectory over 2 years in both intervention arms with a non-enrolled comparison group, using data from the PCORnet Common Data Model at participating sites.

Hypothesis 4: PCORnet analysis will reveal the benefit of both Greenlight approaches (Arms 1 and 2) compared to before Greenlight intervention implementation and the added benefit of Arm 2 (Greenlight Plus) over other approaches.

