2.1 COVID-19 Supplemental Aims

To rapidly respond to the COVID-19 pandemic, the study team received additional funding to conduct a mixed-methods enhancement of the PCORI-funded Greenlight Plus Study. The goal of this study enhancement is: 1) to describe the impact of the COVID-19 pandemic on social drivers of health and 2) to examine the resultant effect of the COVID-19 pandemic on infant growth in a multi-site sample of low income and minority families. This enhancement will provide data on the nature and extent of the social consequences of the COVID pandemic, with a specific focus on early childhood growth and vulnerable populations.

The COVID-19 pandemic has led to an unprecedented number of unemployment claims, increased food and housing insecurity, reduced access to health care and social support programs, a rise in stress and mental health issues, and a higher risk of domestic violence and child abuse.¹⁻³ We know these social drivers of health, particularly during the critical periods of pregnancy, infancy, and early childhood, can have a profound impact on long term health.⁴ Because this is an unprecedented global event, we lack evidence regarding the specific stressors caused by the COVID-19 pandemic and how they will impact child health outcomes. Developing intervention strategies to support families hardest hit by the social consequences of COVID-19 requires understanding barriers that families are facing and the resources they need to address those barriers in real time. In addition, tracking the lasting consequences of this pandemic from a life course perspective will facilitate intervention strategies to support child growth and development.

Using this cohort, and taking advantage of a natural experiment, **we will address the following aims:**

Specific Aim 1: To explore the impact of the COVID-19 pandemic on changes in families' social, emotional, financial, psychological, and healthcare needs by conducting a qualitative study involving repeated interviews among parents who experienced the pandemic at various stages of their infant's life, including "early pandemic" (infant born prior to 3/11/2020), "peak pandemic" (infant born 3/11/2020 – 6/11/2020), and "later pandemic" (infant born after 6/11/2020).

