ARM 2: *Greenlight Plus*: Families randomized to the Greenlight Plus arm will receive the Greenlight Toolkit (identical to Arm 1) *PLUS* a HIT intervention starting at the newborn clinic visit. Prior to randomization, all families will receive basic instructions on how to interact with the text-messaging application (with occasional text messaging used as a retention tool in the control group). After randomization, families in Arm 2 will receive basic instructions on how to access the Greenlight technology platform, which includes the iOTA text-messaging application and a website dashboard (usable on desktop or mobile platform).

The core of the HIT intervention is a text-messaging application, based on the interactive Obesity Treatment Approach (iOTA). iOTA was originally designed for adult patients to induce an energy deficit sufficient to produce weight loss through the modification of routine obesogenic lifestyle behaviors. iOTA was created in response to: 1) the frequent finding of poorer weight loss outcomes and less intervention engagement among underserved, minority populations,¹³⁴ and 2) the difficulty in translating traditional intervention approaches (e.g., in-person counseling, strict calorie/physical activity targets) to the community health center setting. These traditional approaches are cognitively complex, require considerable literacy/numeracy skills, and make inherent assumptions about participants' ability to access healthful resources. In contrast, iOTA is straightforward and does not require expert knowledge or expensive resources. iOTA's adaptive design is prime for self-management of behavioral goals for parents of infants and toddlers. Behind the scenes, the iOTA system is sophisticated, but uses low-cost, easy-to disseminate digital health software systems. It relies on a series of interconnected algorithms and content libraries. An algorithm tailors feedback, selecting content from a vast content library. From our skills training library, we send materials to assist behavior change efforts.

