8.3 Measures related to the COVID-specific aims

First, we will conduct a qualitative evaluation of social needs facing low-income families and the degree to which current social supports are adequate to address those needs. Trained interviewers will conduct 1:1 interviews with the primary parent in English or Spanish. They will follow an interview guide grounded in the social ecological model to explore the social and behavioral impacts of COVID19 (Appendix 1). These interviews will occur three times, during July-September 2020, December 2020-February 2021, and April 2021-June 2021. Participants already enrolled in the parent study will be eligible to participate. Recruitment for the qualitative study will occur during previously scheduled data collection visits (i.e., well-child checks) for the parent study.

Second, we will conduct a birth-cohort analysis by engaging the participants who were recruited prior to the pandemic onset (N=117) and those that will be recruited over the next 9 months (N=783, for total N=900). We will add survey measures that are informed by theory (e.g., newly developed coronavirus impact scale, measures of family resilience, etc.)^{143,144} and the qualitative interviews in Aim 1. All newly proposed measures will be obtained at a COVID baseline and the 24-month follow-up. The Coronavirus impact scale will be collected at all additional timepoints beginning at 2 months.

COVID-19 Related Measures (Newly developed, obtained from NIH repository)	
Coronavirus Impact Scale	Measures COVID-19 impacts including changes to daily routines, family income, access to healthcare, access to social supports, family discord, etc. (12 items).
COVID-19 exposure and family impact survey (CEFIS)	Measures COVID-19 stress across multiple domains including number of affected family members, degree of social isolation, and effects of parenting, financial hardship, access to food/medication, etc. (37 items)
Duke COVID-19 Survey (Stress/Anxiety due to COVID-19)	Measures changes in sleep, anxiety, depressive symptoms. (9 items)
Family Assessment Device	General Functioning Sub-Scale. (12 items) ¹⁴⁶
FRAS Subscale	Measures utilization of social and economic resources (11 items)

COVID-19 Related Self-Efficacy	Measures self-efficacy to respond to the psychological and social challenges of the pandemic. (10 items)
--------------------------------	--

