We will also compare the participants in the current trial to an external cohort of children not enrolled in the current Greenlight Plus Study (GPS). At each site, the standard Greenlight (GL) Intervention will be administered to those randomized to it and to those who did not participate in the study. We will collect additional data that includes: 1) children who were not exposed to the present Greenlight Plus Study interventions because they were born in the years preceding GPS, and 2) children who were exposed to the Greenlight intervention because they received care during the GPS study time but were not enrolled in GPS.

Power calculations: We conducted simulation-based calculations to estimate the power for the primary outcome. We generated the Greenlight and Greenlight Plus data using linear mixed models of observed data in the original Greenlight study. From these

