11.3 Analysis plan for COVID-related aims

COVID Aim 1 (qualitative): All interviews will be transcribed. Transcriptions will then be coded using a hierarchical coding system by two independent reviewers. We will identify themes by a process of repeated review. Based on those themes, we will develop a schema to describe the social effects of the pandemic.

COVID Aim 2 (quantitative): To account for regional differences, we will calculate the difference between the child's date of birth and the time public health quarantine measures were instituted in each enrollment city. The primary outcome will be child growth rate over 6 months (collected as a part of the primary study). We will model the primary outcome using a linear mixed effects model, controlling for baseline demographics, study site, and intervention condition.

Finally, we will study the moderating effect of the COVID pandemic on the original intervention by including an interaction term between intervention assignment and the

timing of the pandemic as defined above. We hypothesize that for families who experience social isolation, our text-messaging based intervention may be more effective.

12. Amendments to the Study Protocol:

All amendments to the Study Protocol will be approved by the Steering Committee, DSMB, and IRB. All amendments will be appended to the study protocol with the rationale for the change and the date on which the change was implemented.

The study protocol was initially approved by the Steering Committee and DSMB on 9/3/19.

Amendment 1 (3/26/2020): IFSQ, previously planned to be administered in full at the 6-month time point, was split into two measures. The belief section and 7 behavior questions will be administered at the 6-month time point, and 11 additional behavior questions will be administered at the 12-month time point. These changes were made in the table on page 20.

Amendment 2 (8/6/2020):

1. Updated data collection table (table 8.3) to reflect changes to measures at the 9 month, 12 month, 15 month, 18 month, and 24 month data collection timepoints.
New or revised measures included:
 - a. New parent media surveys at 12 and 15 months, including measures of access to broadband internet, parent use of various media types, and “technoference”
 - b. Revised measures of child diet practices at 24 months, to include a shortened, but validated, version of the Child Feeding Questionnaire

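### Aim 4's before/after contrast almost fully aliases Greenlight exposure with the pandemic period, so it cannot support the benefit claimed in Hypothesis 4

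*Combined protocol and SAP*

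**What the plan says.** Hypothesis 4 (section 2) states that "PCORnet analysis will reveal the benefit of both Greenlight approaches (Arms 1 and 2) compared to before Greenlight intervention implementation". It also claims an added benefit of Arm 2 over other approaches.

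Section 11.1 defines two external groups. The first is unexposed because its children were "born in the years preceding GPS". The second is "children who were exposed to the Greenlight intervention because they received care during the GPS study time but were not enrolled in GPS". The same paragraph says of all the clinics that "the standard Greenlight (GL) Intervention will be administered to those randomized to it and to those who did not participate in the study". Section 7.2 gives Arm 2 the same toolkit as Arm 1, plus the technology component.

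On timing, section 12 records: "The study protocol was initially approved by the Steering Committee and DSMB on 9/3/19". Section 2.1 uses 3/11/2020 as the pandemic boundary and sets the goal "to examine the resultant effect of the COVID-19 pandemic on infant growth". Section 8.3 counts 117 participants recruited before onset and 783 still to be recruited, 900 in all.

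For Aim 4, section 11.1 gives no model, covariates, birth-year limits, calendar-time term or pandemic term. Section 11.3 does model pandemic timing, but only within the trial cohort.

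**The concern.** A before/after comparison attributes to the intervention anything else that changed between the two periods. Here a large change falls almost exactly at the boundary, and the protocol itself treats it as a possible influence on infant growth. No concurrent group goes without Greenlight, so a period effect cannot be subtracted out.

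Aim 4 is the only planned comparison of Greenlight with no study Greenlight. If the before/after difference is read as Hypothesis 4 words it, a shift in growth between periods could be published as a benefit of Greenlight, or could hide one.

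**Working it through.** The plan states no sample size, effect size, significance level or power for Aim 4, so it has no figure to reproduce. The check rests on who was exposed to what, on dates, and on an illustration.

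**Exposure by group**

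| Group | Study Greenlight | Calendar period |
|---|---|---|
| Arm 1 | Yes | Approval date onward |
| Arm 2 | Yes, plus technology | Approval date onward |
| Not enrolled, in care during the study | Yes | Approval date onward |
| Born in the years before the study | No | Earlier; limits not given |

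The only group without Greenlight is historical.

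**Dates for enrolled children.** The first enrolment date is not stated. I take the approval date, 9/3/2019, as the earliest; a later start makes the overlap more complete.

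- 9/3/2019 to 3/11/2020 is 190 days, or 190/730 = 26% of 24 months. A child born on the approval date has 74% of follow-up after onset.
- The 9-month window opens at day 226 (Table 8.3): 9/3/2019 + 226 days = 4/16/2020. A child born 21 days before approval, the current age limit for enrolment, reaches day 226 on 3/26/2020. Both dates are after onset.
- The 24-month window opens at day 636: 9/3/2019 + 636 days = 5/31/2021, more than 14 months after onset.
- 117/900 = 13% were recruited before onset and 783/900 = 87% after. Only the 117 can have any pre-onset visits, and only up to about 6 months of age.

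**Dates for historical children.** Those born by 3/12/2018 reach day 730 by 3/11/2020. Children born from about March 2018 to September 2019 have follow-up on both sides of onset, but their clinics were giving Greenlight to non-participants once the study began. They are not a clean group with pandemic exposure and no Greenlight. As worded, the two external groups can also overlap, since a child born before the study may still be in care during it.

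**Illustration on assumed inputs.** Suppose Greenlight has no effect and the period shifts a 24-month outcome by s SD. With n trial children, H historical children and a two-sided 0.05 test:

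SE = √(1/n + 1/H), in SD units; P(significant in the direction of the shift) = Φ(s/SE − 1.96).

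Trial numbers use the 30% attrition of the power section: 900 × 0.70 = 630 for both arms and 450 × 0.70 = 315 for Arm 1. H is assumed. The value 5950 is the section 6 estimate of potentially eligible families, borrowed only as an upper value. Example: n = 630, H = 1000, s = 0.1 gives SE = 0.0509, 0.1/0.0509 = 1.966 and P = Φ(0.006) = 0.50.

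| n | H | SE | s = 0.05 | s = 0.1 | s = 0.2 |
|---|---|---|---|---|---|
| 630 | 1000 | 0.0509 | 16% | 50% | 98% |
| 630 | 2000 | 0.0457 | 19% | 59% | 99% |
| 630 | 5950 | 0.0419 | 22% | 67% | >99% |
| 315 | 1000 | 0.0646 | 12% | 34% | 87% |
| 315 | 2000 | 0.0606 | 13% | 38% | 91% |
| 315 | 5950 | 0.0578 | 14% | 41% | 93% |

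This is a single-time-point calculation that ignores site correlation. It shows the behaviour of the contrast and does not predict a result. A larger historical cohort makes the misattribution more likely.

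**The case against.** Several points on the other side stand.

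- A reader might infer that every enrolled and every concurrent child was followed in the pandemic, so that the two exposures can never be separated. The text does not support that. The concurrent group is defined by receiving care during the study, not by birth date, so a child of about 20 months in autumn 2019 qualifies and could turn 2 before onset, with only partial Greenlight exposure. The 117 early recruits also have some pre-onset visits.
- A reader might infer that the plan contains an analysis that will certainly misattribute a period effect. Section 11.1 writes no Aim 4 model at all. What can be faulted is the contrast it defines, together with the conclusion that Hypothesis 4 draws from it.
- The documents give no direction or size for a pandemic effect, and section 2.1 says that evidence is lacking. The percentages depend on assumed shifts and cohort sizes. Using all 900 children without attrition would overstate them, and would not match the Arm 1 question.
- COVID Aim 2 relates birth timing to 6-month growth and so says something about the period. But it covers 6 months only, in children who all receive Greenlight, and is not linked to Aim 4.
- Arm 2 versus Arm 1 is randomized and concurrent. Arm 2 versus concurrent non-enrolled children shares calendar time, though it is open to selection.

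These points narrow the finding. None of them supplies a Greenlight-free group in the pandemic period, or enrolled children with pre-pandemic visits at 9 to 24 months.

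**Conclusion.** The point holds for the before/after part of Hypothesis 4. From the 9-month visit onward, enrolled children have no pre-onset measurements and the comparison has no clean post-onset group without Greenlight. Exposure and period are therefore almost, though not perfectly, aliased for the 24-month trajectory, and no adjustment is planned.

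The possible size is unknown. On the stated assumptions, a 0.1 SD period shift with no Greenlight effect would be significant about 50–67% of the time for both arms together and 34–41% for Arm 1 alone. The date argument assumes that enrolment did not begin before protocol approval.

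Aim 4 is a secondary aim. The primary outcome and the other randomized comparisons are not affected.

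**What to change.** 1. Reword Hypothesis 4 and the Aim 4 conclusion. Report the before/after contrast as a descriptive difference between calendar periods, not as a benefit of Greenlight. Rest the added benefit of Arm 2 on the randomized Arm 2 versus Arm 1 comparison.
2. As a sensitivity analysis only, state birth-year limits for the historical group, fit a birth-quarter trend in the pre-trial children, and add a time-varying term for measurement before or after 3/11/2020. Say in the plan that children born about March 2018 to September 2019 may have received some Greenlight. Say also that restricting to pre-onset measurements leaves at most 117 trial children and informs only about the first 6 months of age, not the 24-month outcome.

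The first change costs a few sentences and is sufficient by itself to remove the unsupported inference. The second needs birth and measurement dates; the documents do not list the extracted fields, but defining these groups and building trajectories already requires such dates. The real cost is a weaker claim for Aim 4.

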11.2. Site-specific Data Capture

At all major data collection time points, data are entered directly into a REDCap database. REDCap is a secure, web-based data management system that allows direct entry of participant data (e.g., measurements, responses to survey questions, etc.) into an electronic format. This direct entry system facilitates the process of downloading and transferring data to the research coordinating unit (RCU). Other REDCap features include built-in data validity checks as well as automated export procedures for downloads to Excel and common statistical packages (SPSS, SAS, Stata and R).

11.2.1. Data collection and recording

Research material obtained from human subjects will primarily involve the collection of self-reported data from surveys and questionnaires from Caregivers and Pediatric Residents. In addition, the weight and height of each child will be collected at each well-child visit. For the 24-month timepoint, a child's height and weight will be collected from another visit at the same clinic, or at another sub-specialty clinic that shares the same EHR, if a well-child visit is not available during the timepoint window. Measurements will only be used if the child comes in for a visit that would not affect their weight (e.g. ear infection). These measures would normally be collected for these visits and, as such, do not represent increased burden or risk on the child or family participating in the study. Finally, medical record review will occur during the first two years of the child's life to obtain information about the child's use of clinical services during the course of the

study. All information gathered will be recorded on paper records or directly into REDCAP and will be maintained in the REDCAP study database.

11.2.3. Database closure

During active data collection, a copy of the REDCap data will be periodically downloaded into an excel file. These files will be housed in a read-only format on a secure server. After data collection is complete, the REDCap database will be moved into inactive status, where all data are still visible but no new entry can be made.

11.2.4. Data security and confidentiality

All data collected on paper will be housed in a locked file cabinet at the offices of the research staff. Access to the files is restricted to study staff. Files will be labeled by the unique participant IDs assigned to each parent-child pair. On REDCap, all files are protected by the need for a user name and password. Through REDCap's user rights function, the data analyst can limit and grant access for specific tools to study staff as needed. Any computerized data will be kept on a secure server at Vanderbilt with limited access and/or in a read-only file. Any material that must be thrown away that involves participant information will be shredded through the document management procedures available at Vanderbilt through Cintas.

11.2.5. Data quality assurance

Many of the features of the web-based REDCap data management system, such as range checks and branching logic, are designed to ensure the quality and completeness of the study data. In addition, all data are manually entered directly into the database on-site, which eliminates data entry errors and greatly reduces the occurrence of skipped data. After every data collection session, the data analyst will review the data entered for both flagged issues noted in data collection and blank answers. These will be corrected as necessary before analysis. Anthropometric measurement error will be reduced through quality checks, which involve replicating, within a small margin of error, 10% of all measurements by another data collector.

